5.4.3. Renal Monitoring

If a subject develops any of the following signs:

- i) haematuria (in the absence of urinary tract infection)
- ii) demonstrates a UPCR>0.5
- iii) demonstrates a >15% decline in eGFR

and findings are confirmed on a second assessment within 48 hours, then the subject should be referred for a nephrology consult.

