5.4.2. QTc Evaluation Criteria

Further monitoring and/or evaluation should be considered in any subject who meets either of the bulleted criteria below:

- QTc >500 msec OR Uncorrected QT >600 msec
- Change from baseline of QTc >60 msec

For subjects with underlying **bundle-branch block**, follow the evaluation criteria listed below:

Baseline QTc with Bundle-Branch Block	Criteria for Further Evaluation and Monitoring of QTc with Bundle-Branch Block
<450 msec	>500 msec
450 to 480 msec	≥530 msec

- The enhanced monitoring criteria are based on an average QTc value of triplicate ECGs. If an ECG demonstrates a prolonged QT interval, two additional ECGs must be obtained over a brief period, and then the averaged QTc values of the 3 ECGs will be used to determine whether the subject meets these criteria.
- The same QT correction formula must be used for each individual subject to determine eligibility for the study, and whether further evaluation and/or monitoring is/are necessary. This formula may not be changed or substituted once the subject has been enrolled.
 - For example, if a subject is eligible for the protocol based on QT interval corrected for heart rate according to Fridericia's formula (QTcF) then QTcF must be used for discontinuation of this individual subject as well.
 - Once the QT correction formula has been chosen for a subject's eligibility, the same formula must continue to be used for that subject for all QTc data being collected for data analysis. Safety electrocardiograms (ECGs) and other non-protocol-specified ECGs are an exception.
- Considerations for further monitoring and evaluation should include the following, as appropriate:
 - Assessment of any relevant symptoms (e.g., presyncope);
 - Follow-up ECGs to assess for resolution of QTc prolongation;
 - Review of concomitant or recently taken medications, including over the counter preparations and herbal supplements
 - Evaluation of electrolytes to include magnesium and potassium

- Referral to urgent care or to an emergency facility for further evaluation and monitoring
- Any other evaluation that may be necessary as determined by the investigator.

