2.2. Study Objective(s) and Endpoint(s)

Objectives		Endpoints		
Primary O	bjectives	Primary Endpoints		
 Evaluate biodistribution of 89Zr- GSK3128349 in regions of interest following IV administration to support future AlbudAb products and the development of a PBPK model. Secondary Objectives 		 Quantitative parameters (including but not limited to 89Zr-GSK3128349 concentration) derived from Positron Emission Tomography – Computer Tomography (PET-CT) data (e.g. Standardised Uptake Values (SUVs)a, volume of Regions Of Interest (ROI) to assess average and total uptake into regions of interest (e.g. liver, kidney, muscle, spleen, heart, lung, bladder, thymus – if feasible -, blood and bone). 		
Secondary	y Objectives	Secondary Endpoints		
 Measu by who radiola future develo Measu mass s suppo a PBP 	The PK of 89Zr-GSK3128349 ole blood, plasma and urine abel detection to support AlbudAb products and the opment of a PBPK model. The PK of GSK3128349 by spectroscopy (MS) to ort the development of PK model.	 Whole blood, plasma and urine radioactivity concentrations and derived pharmacokinetic parameters, as data allows, based on blood, plasma and urine scintillation counting. Plasma concentrations and derived pharmacokinetic parameters. Compare plasma exposure assessments via different GSK3128349 mass spectroscopy 		
		methods.		
3) Measu GSK3 blood	re dosimetry of 89Zr- 128349 from PET scans and radioactivity.	Organ doses (mSv)Effective dose (mSv)		
4) Asses tolerat	s the safety and bility of 89Zr-GSK3128349.	 Adverse events (AEs), serious adverse events (SAEs). Safety laboratory values, proteinuria, electrocardiograms (ECGs) and vital signs. 		
5) Investi levels antibo post-d	igate the presence and of anti-GSK3128349 dies, including pre- and lose.	 Incidence of anti-GSK3128349 antibodies. Serum titres of anti-GSK3128349 antibodies. 		

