8.2.2. Overview of Planned Clinical Laboratory Analyses

The safety analyses will be based on the Safety population, unless otherwise specified.

Table 8 provides an overview of the planned analyses, with further details of data displays being presented in Appendix 8: List of Data Displays.

Table 8 Overview of Planned Clinical Laboratory Analyses

Endpoint / Parameter/ Display Type		Abs	olute	Change from BL			
	Sum	mary	Individual	Sumr	nary	ary Individual	
	Т	F	L	Т	F	L	
Chemistry							
Clinical Chemistry Parameters	Y			Y			
Chemistry Data for Subjects with Abnormalities of Potential Clinical Concern			Y				
Chemistry Data Abnormalities of Potential Clinical Importance			Y				
Hematology							
Hematology Parameters	Y			Y			
Hematology Data for Subjects with Abnormalities of Potential Clinical Concern			Y				
Hematology Data Abnormalities of Potential Clinical Importance			Y				
Urinalysis							
Urine Concentration Data	Y		Y	Y			

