10.6. Appendix 6: Values of Potential Clinical Importance

10.6.1. Laboratory Values

Haematology				
Laboratory Parameter	Units	Category	Clinical Concern Range	
			Low Flag (< x)	High Flag (>x)
		Male		0.54
Hematocrit	Ratio of 1	Female		0.54
		Δ from BL	↓0.075	
	e.//	Male		180
Hemoglobin	g/L	Female		180
		Δ from BL	↓25	
Lymphocytes	x10 ⁹ / L		0.8	
Neutrophil Count	x10 ⁹ / L		1.5	
Platelet Count	x10 ⁹ / L		100	550
While Blood Cell Count (WBC)	x10 ⁹ / L		3	20

Clinical Chemistry				
Laboratory Parameter	Units	Category	Clinical Concern Range	
			Low Flag (< x)	High Flag (>x)
Albumin	mmol/L		30	
Calcium	mmol/L		2	2.75
Creatinine	mmol/L	Δ from BL		↑ 44.2
Glucose	mmol/L		3	9
Magnesium	mmol/L		0.5	1.23
Phosphorus	mmol/L		0.8	1.6
Potassium	mmol/L		3	5.5
Sodium	mmol/L		130	150
Total CO2	mmol/L		18	32

Liver Function			
Test Analyte	Units	Category	Clinical Concern Range
ALT/SGPT	U/L	High	\geq 2x ULN
AST/SGOT	U/L	High	\geq 2x ULN
AlkPhos	U/L	High	\geq 2x ULN
T Bilirubin	µmol/L	High	≥ 1.5xULN
	µmol/L		1.5xULN T. Bilirubin
T. Bilirubin + ALT		High	+
	U/L		\geq 2x ULN ALT

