10.8.10. ICH Listings

ICH : Lis	CH : Listings							
No.	Population	IDSL / TST ID / Example Shell	Title	e Programming Notes				
Subject	Disposition							
1.	All Screened	ES7	Listing of Reasons for Screen Failure		SAC			
2.	Safety	ES2	Listing of Reasons for Study Withdrawal		SAC			
Protoco	ol Deviations							
3.	Safety	DV2	Listing of Important Protocol Deviations		SAC			
4.	All Screened	IE3	Listing of Subjects with Inclusion/Exclusion Criteria Deviations	ting of Subjects with Inclusion/Exclusion Criteria Deviations				
Populat	ions Analysed							
5.	All Screened	SA3a	Listing of Subjects Excluded from Any Population		SAC			
Demogi	raphic and Bas	eline Characterist	tics					
6.	Safety	DM2	Listing of Demographic Characteristics		SAC			
7.	Safety	DM9	Listing of Race		SAC			
Prior an	d Concomitan	t Medications						
8.	Safety	CP_CM3	Listing of Concomitant Medications		SAC			
Exposu	Exposure and Treatment Compliance							

RES117169

ICH : Li	stings				
No.	Population	IDSL / TST ID / Example Shell	Title	Programming Notes	Deliverable [Priority]
9.	Safety	EX3	Listing of Exposure Data		SAC
Advers	e Events				
10.	Safety	CP_AE8	Listing of All Adverse Events		SAC
11.	Safety	AE7	Listing of Subject Numbers for Individual Adverse Events		SAC
12.	Safety	AE2	Listing of Relationship Between Adverse Event System Organ Classes, Preferred Terms, and Verbatim Text		SAC
Serious	and Other Sig	nificant Adverse	Events		
13.	Safety	CP_AE8	Listing of Serious Adverse Events		SAC
14.	Safety		Listing of Reasons for considering as a Serious Adverse Event		SAC
Chemis	try Data				
15.	Safety	LB5	Listing of All Clinical Chemistry Data for Subjects with Abnormalities of Potential Clinical Importance		SAC
16.	Safety	LB5	Listing of Chemistry Abnormalities of Potential Clinical Importance		SAC
Labora	tory Data				
17.	Safety	LB5	Listing of All Haematology Data for Subjects with Abnormalities of Potential Clinical Importance		SAC
18.	Safety	LB5	Listing of Haematology Abnormalities of Potential Clinical Importance		SAC
ECG					
19.	Safety	CP_EG3	Listing of All ECG Values for Subjects with a Value of Potential Clinical Importance		SAC
20.	Safety	CP_EG3	Listing of ECG Values of Potential Clinical Importance		SAC

RES117169

ICH : Li	CH : Listings						
No.	Population	IDSL / TST ID / Example Shell	Title	Programming Notes	Deliverable [Priority]		
21.	Safety	CP_EG5	Listing of Abnormal ECG Findings		SAC		
Vital S	igns						

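### SAP 10.6 does not reliably identify subjects who meet the protocol's own renal criteria, and UPCR has no flag, baseline row, named display or listing

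*Protocol*

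**What the plan says.** **Protocol**
- Section 5.4.3 names three signs: haematuria not explained by urinary tract infection; a subject who "demonstrates a UPCR>0.5"; and one who "demonstrates a >15% decline in eGFR". A sign confirmed on a second assessment within 48 hours leads to a nephrology consult.
- Section 5.4.2 asks for further evaluation to be considered at QTc above 500 msec, uncorrected QT above 600 msec, or "Change from baseline of QTc >60 msec".
- Table 3 lists renal injury first among four risks. Section 7.3.6 prints eGFR beside creatinine in the chemistry panel and puts UPCR under other tests, apart from routine urinalysis.

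**SAP**
- Section 2.2 keeps proteinuria as a secondary safety endpoint: "Safety laboratory values, proteinuria, electrocardiograms (ECGs) and vital signs".
- The section headed "10.6.1. Laboratory Values" has no UPCR, eGFR or urinalysis row. Its one renal limit is a creatinine rise from baseline of more than 44.2, with the unit printed as mmol/L.
- Section 10.6.2 gives absolute limits for QTc (from above 450 msec), PR and QRS. It has no change criterion and no uncorrected QT.
- Section 10.3.2.1 defines baselines for haematology, chemistry, urinalysis, ECG and vital signs. UPCR is not named.
- Table 8 in section 8.2.2 marks an individual listing for its urinalysis row, "Urine Concentration Data". Appendix 8 has summary Tables 4.7 and 4.8 but no urinalysis or UPCR listing among Listings 1-38.
- Listing 15 is titled "Listing of All Clinical Chemistry Data for Subjects with Abnormalities of Potential Clinical Importance". Listing 16 and the ECG value Listings 19-20 are likewise limited by the clinical-importance limits.
- Section 10.3.3 keeps unscheduled visits out of tables and figures and shows them only in listings.

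**The concern.** In the SAP the clinical-importance limits do more than mark values: they decide whose individual chemistry and ECG values are listed. If the limits do not reflect the protocol's own criteria, a subject who met a protocol criterion and was sent for a nephrology opinion need not be identifiable in the planned laboratory displays. The report could then state that no renal value of potential clinical importance occurred.

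This is a first-in-human study of 6-8 subjects, where safety is read subject by subject. Summary tables of that size do not say which subject changed. The 48-hour confirmatory repeat adds to the problem. It will usually be unscheduled, so section 10.3.3 sends it to listings only, and for UPCR and urinalysis Appendix 8 has no listing to receive it.

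**Working it through.** The plan gives no figure of its own to reproduce. The check compares the criteria and then works out what the SAP limits would catch.

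**Step 1. Criteria side by side**

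| Protocol criterion | SAP 10.6 | Individual listing in Appendix 8 |
|---|---|---|
| Haematuria, no urinary tract infection (5.4.3) | none | none |
| UPCR >0.5 (5.4.3) | none | none |
| eGFR fall >15% (5.4.3) | none; creatinine rise >44.2 only | only if some chemistry limit is met |
| QTc >500 msec (5.4.2) | covered by the band from 500 msec | Listings 19-20 |
| QTc rise >60 msec (5.4.2) | none; absolute QTc only | only if an ECG limit is met |
| Uncorrected QT >600 msec (5.4.2) | none | only if an ECG limit is met |

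Listing 27 concerns urine, but it holds ⁸⁹Zr-GSK3128349 concentrations and not protein, creatinine or blood.

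**Step 2. The creatinine limit as printed**

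Assume a baseline of 0.08 mmol/L (80 µmol/L). Then 44.2 / 0.08 = 552.5. The rise would have to be about 550 times baseline, so the flag could never be raised.

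**Step 3. The creatinine limit if µmol/L is meant**

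The protocol names the CKD-EPI equation but does not print it, so the following are assumptions: eGFR proportional to creatinine^(-k), k from 1.0 to 1.2, baseline creatinine b from 60 to 110 µmol/L.

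- eGFR fall at the SAP limit = 1 - ((b + 44.2)/b)^(-k)
- Creatinine rise that gives a 15% fall = b × (0.85^(-1/k) - 1)

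| b (µmol/L) | Fall at +44.2, k = 1.0 | Fall at +44.2, k = 1.2 | Rise for 15% fall, k = 1.0 | Rise for 15% fall, k = 1.2 |
|---|---|---|---|---|
| 60 | 42.4% | 48.4% | 10.6 | 8.7 |
| 80 | 35.6% | 41.0% | 14.1 | 11.6 |
| 100 | 30.7% | 35.5% | 17.6 | 14.5 |
| 110 | 28.7% | 33.3% | 19.4 | 16.0 |

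The SAP limit is reached at a fall of about 29-48%. The protocol criterion is reached at a creatinine rise of about 9-19 µmol/L. Falls between 15% and 29-48% meet the protocol criterion without a SAP renal flag.

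**Step 4. QTc rise**

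A rise above 60 msec escapes the limit of 450 msec only if the final value is 450 or less, so baseline must be below 450 - 60 = 390 msec. Example: 380 to 445 msec is a rise of 65, and 445 is not above 450. From a baseline of 390 to 450 (450 being the entry limit), any rise above 60 ends above 450 and is flagged, though as an absolute value and not as a rise.

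**Step 5. Uncorrected QT**

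With the SAP 10.4.3 formulas, QT of 600 and QTc of 450 imply RR = (600/450)³ × 1000 ≈ 2370 msec (Fridericia) or (600/450)² × 1000 ≈ 1778 msec (Bazett). In heart rate, 60000/RR, that is about 25 or 34 beats per minute. At higher rates, a QT above 600 msec also exceeds the QTc limit, so this omission matters little in practice.

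**The case against.** The strongest reply is that these are different tools. Protocol 5.4.2 and 5.4.3 guide action at the site, with averaged triplicate ECGs or a confirmatory result. The SAP limits are reporting ranges, and neither document says they must match. That stands: this is a reporting gap and not a contradiction between protocol and SAP. The one direct inconsistency is within the SAP, between Table 8 and Appendix 8.

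A reader might infer that a subject meeting a protocol criterion is never flagged or listed. The documents do not support that:
- A large creatinine rise would meet the SAP limit if µmol/L is meant.
- Meeting any other chemistry limit puts all of that subject's chemistry into Listing 15.
- Most QTc rises above 60 msec from baselines near the entry limit end above 450 msec and are listed.
- Laboratory or ECG results judged clinically significant are adverse events (Protocol 12.3.1) and go to Listing 10. This depends on the investigator's judgement, so it is a possible route and not an assured one.
- eGFR belongs to the chemistry panel, so it plausibly has a Day -1 baseline and a place in Table 4.4, in aggregate.
- Table 8 shows that an individual urinalysis listing was intended. Whether it would include UPCR is unclear, because the protocol lists UPCR separately.

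A reader might also call renal injury the study's main risk. Table 3 puts it first but does not rank the four risks, and ties the renal finding to repeat dosing beyond 4 weeks in mice, whereas this is a single-dose study.

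Finally, a reader might want to delete SAP limits for analytes outside the routine panel. Protocol 5.4.2 mentions magnesium in QTc evaluation and 7.3.6 allows additional tests, so that does not follow.

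**Conclusion.** The gap is real and should be closed, chiefly on the renal side.

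The UPCR part rests on no assumption: a secondary endpoint measure has no flag at any value, no baseline row, no named display and no listing in Appendix 8. The absence of an eGFR criterion is equally plain. Its size depends on the assumptions in Step 3: falls from 15% to roughly 29-48% raise no renal flag if µmol/L is meant, and no fall of any size raises one if the printed unit is taken literally. A narrower range would need the coefficients of a particular CKD-EPI version, which the documents do not give.

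The QTc part is minor: it concerns baselines below 390 msec, and the missing uncorrected QT criterion adds little.

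The defensible conclusion is that such subjects are not reliably identified. The primary PET objective is unaffected.

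**What to change.** 1. Reconcile SAP 10.6 with Protocol 5.4.2 and 5.4.3 by adding a display that identifies each subject meeting those criteria exactly as the protocol words them, with the confirmatory result: the three renal signs, QTc change above 60 msec and uncorrected QT above 600 msec. No new threshold is needed. In particular, haematuria should keep its urinary tract infection qualifier and not become a bare dipstick result.
2. Add to Appendix 8 the individual urinalysis listing that Table 8 marks. It should cover UPCR, eGFR and urinalysis for all subjects, including unscheduled repeats.
3. Add a UPCR row to 10.3.2.1 (Day -1 is the scheduled pre-dose value) and state that UPCR is included in Tables 4.7 and 4.8.
4. Check the creatinine unit in 10.6.1 against its source and correct it.

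The other limits in 10.6.1 can stay. The cost is a few SAP rows and one or two extra listings for 6-8 subjects. The protocol already schedules the measurements.

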5.5. Subject and Study Completion

A completed subject is one who has completed all phases of the study including the follow-up visit.

The end of the study is defined as the last subject's last visit.

6. STUDY TREATMENT

The term 'study treatment' or ⁽⁸⁹Zr-GSK3128349' is used throughout the protocol to describe the drug product, which is a mix of ⁸⁹Zr labeled and unlabelled GSK3128349 received by the subjects as per the protocol design. Details of ⁸⁹Zr labelled GSK3128349 can be found in the relevant non Investigational Medicinal Product (IMP) document.

Product name:	⁸⁹ Zr-GSK3128349						
Formulation	50 mM sodium acetate buffer and 200 mM sucrose at pH						
Description:	5.20-5.80, associated with about 15 MBq of radioactivity.						
Dosage Form:	Solution for IV administration						
Unit Dose	Approximately 10 mL of 0.1mg/mL ⁸⁹ Zr-GSK312834						
Strength							
Dose level	1 mg						
Route/	IV as a continuous infusion over 20 mins						
Administration/							
Duration:							
Dosing	Single dose						
Instructions:							
Physical	Liquid in 50mL vial						
Description:							
Manufacturer/	VUMC, Amsterdam						
Source of							
procurement:							

6.1. Treatment Assignment

Subjects will be identified by a unique subject number at screening that will remain consistent for the duration of the study. Upon completion of screening subjects will be enrolled and will receive 1 mg of ⁸⁹Zr-GSK3128349. There will be no placebo in this study.

There are no randomisation requirements for the study. However, for internal study reporting, subjects will be assigned to randomisation numbers in accordance with the randomisation schedule generated by Clinical Statistics, prior to the start of the study, using validated internal software.

6.2. Blinding

This will be an open-label study.

6.3. Packaging and Labeling

The contents of the label will be in accordance with all applicable regulatory requirements.

6.4. Preparation/Handling/Storage/Accountability

A full description of the method and materials required for administration of ⁸⁹Zr-GSK3128349 will be provided in the Study Reference Manual (SRM).

Study treatment must be dispensed or administered according to procedures described in the SRM. Only subjects enrolled in the study may receive study treatment. Only authorized site staff may supply or administer study treatment. All study treatment must be stored in a secure area with access limited to the investigator and authorized site staff. Storage instructions for all study treatments supplied by GSK (including study product as well as prepared solutions) are provided in the SRM. Maintenance of a temperature log (manual or automated) is required.

Under normal conditions of handling and administration, study treatment is not expected to pose significant safety risks to site staff. Take adequate precautions to avoid direct eye or skin contact and the generation of aerosols or mists. In the case of unintentional occupational exposure notify the monitor, Medical Monitor and/or GSK study contact.

A Material Safety Data Sheet (MSDS)/equivalent document describing occupational hazards and recommended handling precautions either will be provided to the investigator, where this is required by local laws, or is available upon request from GSK.

6.5. Treatment of Study Treatment Overdose

For this study, any dose of ⁸⁹Zr-GSK3128349 over and above the dose specified in the protocol will be considered an overdose.

GSK does not recommend specific treatment for an overdose. The investigator or physician in charge of the subject at the time will use clinical judgment to treat any overdose.

6.6. Treatment after the End of the Study

Subjects will not receive any additional treatment from GSK after completion of the study because only healthy volunteers are eligible for study participation.

6.7. Lifestyle and/or Dietary Restrictions

6.7.1. Contraception Requirements

Male subjects with female partners of child-bearing potential must use one of the following contraceptive methods for 100 days post dose of study treatment. Investigators are responsible for consulting with subjects on selection of contraceptive methods.

- Abstinence, defined as sexual inactivity consistent with the preferred and usual lifestyle of the subject. Periodic abstinence (e.g. calendar, ovulation, symptothermal, post-ovulation methods) and withdrawal are not acceptable methods of contraception
- Condom plus partner use of a highly effective contraceptive (see list below).

Highly Effective Contraceptive Methods with a Failure Rate of < 1%

- Oral contraceptive, either combined or progestogen alone
- Injectable progestogen
- Implants of etonogestrel or levonorgestrel
- Percutaneous contraceptive patches

6.7.2. Caffeine, Alcohol, and Tobacco

Subjects will abstain from alcohol for 48hr before each visit to the clinic and during the in-house stay.

Subjects who use tobacco products will be instructed that use of nicotine-containing products (including nicotine patches) will not be permitted while they are in the Clinical Unit.

6.7.3. Activity

Subjects must refrain from strenuous exercise for approximately 72 hours before all study visits.

6.8. Concomitant Medications and Non-Drug Therapies

6.8.1. Permitted Medications and Non-Drug Therapies

Paracetamol or Acetaminophen, at doses of ≤ 2 grams/day is permitted for use. Other concomitant medication may be considered on a case by case basis by the GSK Medical Monitor.

6.8.2. Prohibited Medications and Non-Drug Therapies

Subjects must abstain from taking prescription or non-prescription drugs, within 7 days or 5 half-lives (whichever is longer) prior to the first dose of study treatment until completion of the follow-up visit, unless in the opinion of the Investigator and sponsor the medication will not interfere with the study.

7. STUDY ASSESSMENTS AND PROCEDURES

Protocol waivers or exemptions are not allowed with the exception of immediate safety concerns. Therefore, adherence to the study design requirements, including those specified in the Time and Events Table, are essential and required for study conduct.

This section lists the procedures and parameters of each planned study assessment. The exact timing of each assessment is listed in the Time and Events Table Section 7.1. Detailed procedures for obtaining each assessment may be provided in the Study Reference Manual (SRM), where necessary. Whenever vital signs, 12-lead ECGs and blood draws are scheduled for the same nominal time, the assessments should occur in the following order: 12-lead ECG, vital signs, blood draws. The timing of the assessments should allow the blood draw to occur at the exact nominal time.

The timing and number of planned study assessments, including: safety, pharmacokinetic or pharmacodynamic/biomarker assessments may be altered during the course of the study based on newly available data (*e.g.* to obtain data closer to the time of peak plasma concentrations) to ensure appropriate monitoring. The timing of PET-CT scans may be changed but not the maximum number of four PET-CT sessions. The change in timing or addition of time points for any planned study assessments must be approved and documented by GSK, but this will not constitute a protocol amendment. The Institutional Review Board (IRB)/ Independent Ethics Committee (IEC) will be informed of any safety issues that require alteration of the safety monitoring scheme. No more than 500 mL of blood will be collected within a 56 day period as per exclusion criteria 19 (Section 5.2), including any extra assessments that may be required.

RES117169

